A mechanism for increased AS in the uninjured population is over activation of the renin-angiotensin-aldosterone system (RAAS). Angiotensin II (ANG II), a hormone produced through RAAS, modulates vascular stiffness by reducing elastin, promotes collagen formation and increases oxidative stress. Due to decentralized cardiovascular autonomic control, individuals with SCI have a heightened reliance on RAAS to maintain and stabilize blood pressure (BP), especially during an orthostatic challenge. **Participants:** A total of 33 subjects, 22 individuals with SCI and 11 age-matched uninjured controls. **Objectives:** To study the hazardous effects of a highly activated RAAS on vasculature, the participant will be placed on a tilt table in the supine position and progressively tilted (30°, 45 ° and 60 ° for 10 minutes at each angle of tilt). PWV will be measured during supine and hormonal assessments (active plasma renin) will be assessed at supine and 60 degree tilt to determine if RAAS specific hormones contribute to increased AS in each cohort. The study aims are: 1) To investigate the influence of orthostatic change of BP and NE responses to orthostasis; and 2) To determine if increased reliance on the RAAS for orthostatic BP regulation contributes to differences in supine AS in individuals with SCI.

SPECIFIC AIMS:

Aim 1: *To investigate the influence of orthostatic change in BP on plasma renin responses to HUT.*

Hypothesis 1A: There will be an inverse relationship between the change in BP and change in plasma renin from supine rest to 60°HUT in individuals with high-level SCI.

Hypothesis 1B: There will be no relationship between the change in BP and change in plasma renin from supine rest to 60° HUT in persons with low-level SCI and uninjured controls.

Orthostatic Blood Pressure and Arterial Stiffness in Persons with Spinal Cord Injury: The Effect of the Renin-Angiotensin-Aldosterone System

Aim 2: To investigate the influence of orthostatic change in BP and NE on the RAAS responses to HUT.

Hypothesis 2A: There will be a linear relationship between the change in orthostatic BP and change in plasma NE concentration from supine rest to 60° HUT.

Hypothesis 2B: Plasma renin activity will be inversely related to plasma NE concentrations during HUT in persons with SCI.

Aim 3: To determine if increased reliance on the RAAS for orthostatic BP regulation contributes to differences in supine AS.

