Orthostatic Blood Pressure and Arterial Stiffness in Persons with Spinal Cord Injury: The Effect of the Renin-Angiotensin-Aldosterone System

and serum aldosterone levels were comparable with baseline levels. We speculate that this may be related to a reliance on RAAS for orthostatic BP maintenance, which may have detrimental effects on AS[24]. Groothuis et al. (2010) demonstrated that ANG II contributed to increased supine leg vascular resistance in individuals with thoracic injuries (T4-T12), but did not contribute to AS in controls[44]. Although increased AS has been reported in individuals with SCI, controversy abounds and additional evidence is needed to gain a better understanding of impact of morphologic and physiologic vascular adaptations that occur following SCI on orthostatic BP regulation and AS.

SIGNIFICANCE OF RESEARCH:

Evidence has shown that PWV is increased 2-3 m/s in persons with SCI compared to able-bodied individuals [45, 46] which corresponds a staggering 40 year acceleration of age-related cardiovascular decline[47]. Evidence of causality suggests that decreases in AS, subsequent to administration of ARBs or ACE inhibitors, reduced vascular remodeling and decreased the risk of myocardial infarction, stroke and cardiovascular mortality in the uninjured population [33]. Additionally, the effects of OH on AS have not been studied in the SCI population, even though, persistent and episodic OH have been associated with elevated risk of stroke and cognitive deficits, including memory, processing speed and executive function in the uninjured population[48-51]. Documenting the impact of the RAAS on AS in the SCI population, will provide a necessary step in initiating a change in clinical treatment of hypotension and OH, which may lead to improved regulation and preservation of cardiovascular health and longevity.

RESEARCH DESIGN & METHODOLOGY:

Subjects– 22 individuals with SCI and 11 age-matched non-SCI controls will be recruited for eligibility to participate in the study. Individuals with SCI will be recruited from the Northern New Jersey SCI Model (NNJSCIS) System database, which contains over 1000 people with traumatic SCI. The control subjects will be recruited from prior study enrollment at Kessler Foundation and hospital personnel.

Inclusion Criteria:

- All subjects:
 - Between ages 21 and 70 years old.
- Additional Inclusion Criteria: SCI subjects:
 - Traumatic injury,
 - High-level injury: C1-T1 and Low-level injury: T6-T12,

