Statistical Analysis: To determine the relationship between change in BP and NE, we will use Pearson's correlation coefficient or Spearman's correlation coefficient with alpha. The independent variable is change in SBP from supine rest to 60° HUT and the dependent variable is change in NE from supine rest to 60° HUT. The alpha level will be set at 0.05.

Aim 3: *To determine if increased reliance on the RAAS for orthostatic BP regulation contributes to differences in supine AS.*

Hypothesis 3A: There will be significant group differences for change in plasma renin during HUT, in that plasma renin will be significantly increased during HUT in participants with high-level SCI, but will remain unchanged in individuals with low-level SCI and uninjured controls.

Statistical Analysis: Differences in change in plasma renin during HUT between groups will be analyzed using univariate group by ANOVA, with the interaction effect being the statistical effect of interest. The alpha level will be set at 0.05. The G*Power calculations indicate that with a total sample size of 33, there will be a power = 0.8.13 to detect the effect size.

Hypothesis 3B: Change in plasma renin during the HUT maneuver will be directly associated with supine PWV in individuals with high-level SCI.

Hypothesis 3C: There will be no relationship between the change in plasma renin during the HUT maneuver and supine PWV in persons with low-level SCI and uninjured controls.

Statistical Analysis: To determine the relationship between change in plasma renin and supine PWV, we will use Pearson's correlation coefficient or Spearman's correlation coefficient with alpha. The independent variable is change in renin from supine rest to 60° HUT and the dependent variable is PWV during supine rest. The alpha level will be set at 0.05.

Orthostatic Blood Pressure and Arterial Stiffness in Persons with Spinal Cord Injury: The Effect of the Renin-Angiotensin-Aldosterone System

STUDY COMPENSATION:

Subjects will receive \$100 for their participation.

PUBLICATION OF RESEARCH:

It is anticipated that the observations made in this study will be presented at National meetings and will be submitted for publication in peer-reviewed journals, including those in the fields of Spinal Cord Medicine.

COST ANALYSIS:

Kessler Foundation will be not responsible for any costs associated with this project. This protocol will be funded by the NJ Commission on Spinal Cord Research (CSCR18FEL010).

REFERENCES:

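### Aim 3 plans no comparison of the renin–PWV relation between groups, and a non-significant correlation in about 11 people cannot show the absence of a relationship that Hypothesis 3C predicts

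*Combined protocol and SAP*

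**What the plan says.** Aim 3 in the DATA ANALYSIS section is: "To determine if increased reliance on the RAAS for orthostatic BP regulation contributes to differences in supine AS". Three hypotheses sit under it.

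- **3A** concerns renin alone. It predicts a rise in high-level SCI, while renin "will remain unchanged in individuals with low-level SCI and uninjured controls". The analysis reads: "Differences in change in plasma renin during HUT between groups will be analyzed using univariate group by ANOVA".
- **3B** predicts: "Change in plasma renin during the HUT maneuver will be directly associated with supine PWV in individuals with high-level SCI".
- **3C** predicts "no relationship between the change in plasma renin during the HUT maneuver and supine PWV in persons with low-level SCI and uninjured controls".

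3B and 3C share one analysis paragraph, which names a Pearson or Spearman coefficient at alpha 0.05 and then says: "The independent variable is change in renin from supine rest to 60° HUT and the dependent variable is PWV during supine rest". It has no group term and does not itself say that the correlation is run by group; that follows from the hypotheses. PWV appears in the analysis section only as the dependent variable of this correlation.

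On numbers, "22 individuals with SCI and 11 age-matched non-SCI controls will be recruited". The division of the 22 into high-level and low-level injury is not given.

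**The concern.** Taken together, 3B and 3C describe a relation that is present in one group and absent in the other two. The plan offers only separate correlations to address this, which leaves two gaps.

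- A significant r in one group beside a non-significant r in another does not show that the two correlations differ.
- 3C predicts a null. With about 11 people, failing to reject r = 0 is the likely outcome even when a moderate correlation exists. The plan sets no bound on how large an r would still count as no relationship.

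If the three results are read side by side, the study could report that renin is linked to stiffness only in high-level SCI when the link is the same everywhere. It could also report no relationship in the comparison groups when the data are compatible with a strong one.

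**Working it through.** **Inputs.** From the documents: 22 SCI, 11 controls, alpha 0.05. Assumed: 11 high-level and 11 low-level subjects, two-sided tests, bivariate normality, complete tilt data. The only power statement in the plan belongs to the 3A ANOVA on renin. It gives no effect size, so it cannot be reproduced, and this point does not rest on it.

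**1. What one group can show (n = 11).** Critical r = t/√(n−2+t²) with t(9) = 2.262, so 2.262/√(9+5.117) = 0.602. The 95% CI for an observed r of 0 is tanh(±1.96/√8) = ±0.60. Simulated power at true r = 0.5 is 0.365, so a correlation of that size is non-significant about 63% of the time.

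**2. How often the predicted pattern appears.** The pattern is: high-level significant and positive, both other groups non-significant. Let p be the power in one group. The few significant negative results matter only at the smallest r.

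- Same r in all groups: about p(1−p)². At r = 0.5, 0.365 × 0.635² = 0.147.
- 3B and 3C true (r in high-level, 0 elsewhere): p × 0.95². At r = 0.5, 0.365 × 0.9025 = 0.329.

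| True r | Same r in all groups | 3B/3C true | Ratio |
|---|---|---|---|
| 0.3 | 0.104 | 0.129 | 1.2 |
| 0.4 | 0.136 | 0.210 | 1.5 |
| 0.5 | 0.147 | 0.328 | 2.2 |
| 0.6 | 0.115 | 0.484 | 4.2 |
| 0.7 | 0.052 | 0.661 | 12.7 |

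The table is from simulation (400,000 draws per group). The split matters: with 14 high-level and 8 low-level subjects the same-r column runs from 0.10 to 0.22; with 8 and 14 it runs from 0.02 to 0.09.

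**3. What a direct contrast would give.** On the Fisher z scale, SE = √(1/8+1/8) = 0.5 and the 95% half-width is 1.96 × 0.5 = 0.98. Against a comparison r of 0, the high-level r must exceed tanh(0.98) = 0.75 for the interval to exclude zero. For r = 0.5 v 0, atanh(0.5)/0.5 = 1.10 and power is 0.20. For 0.7 v 0, 0.867/0.5 = 1.73 and power is 0.41.

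**4. Why the renin SD and slopes belong beside it.** 3A expects renin to be unchanged in the comparison groups, so a smaller spread there is plausible, though not shown. With a common slope, the comparison r is bs/√((bs)²+1−b²), where b is the high-level r and s the SD ratio. For b = 0.5 and s = 1/3 (an assumption), this is 0.167/√(0.028+0.75) = 0.19. The predicted pattern then appears with probability 0.305, almost the 0.328 seen when 3B and 3C are true, although the slope is the same in every group.

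**5. PWV by group (secondary).** SIGNIFICANCE OF RESEARCH cites a PWV 2–3 m/s higher in SCI and gives no SD. Assuming 1.5 to 3 m/s, a pairwise 95% half-width is 2.042 × SD × √(2/11), which is 1.3 to 2.6 m/s. If both SCI groups are raised by 2 m/s, a three-group ANOVA has power 0.88 to 0.32.

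**The case against.** The strongest reply is that the plan states no rule for combining 3B and 3C. They are separate hypotheses, and a significant 3B would support an association within high-level SCI with no contrast at all. The Objectives paragraph even words the purpose as "to determine if RAAS specific hormones contribute to increased AS in each cohort", which within-group correlations address directly. All of this stands, and it makes the harm conditional on the results being read side by side. It does not rescue 3C, whose prediction cannot be established by a non-significant r at this size.

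A reader might infer that the plan can never support a group-specific conclusion. The figures do not bear that out: at a true r of 0.6 or 0.7 the predicted pattern is 4.2 or 12.7 times as likely under 3B/3C as under a common r. The accurate statement is that the plan does not test specificity.

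A reader might also infer that Aim 3 fails without a PWV comparison against controls. The documents do not support this either. The Objectives paragraph words the same aim as concerning people with SCI, raised stiffness in SCI is presented as background, and none of 3A to 3C predicts a PWV group difference.

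Finally, the added contrasts are underpowered. That is true, and it is why they should be estimates rather than tests.

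**Conclusion.** The concern holds in a limited form. Aim 3 lists no comparison of the renin–PWV relation between groups, and 3C cannot be shown by non-significance in groups of about 11. A common r of 0.3 to 0.6 would still produce the predicted pattern in 10% to 15% of studies. At r = 0.3 to 0.4 that pattern is only 1.2 to 1.5 times as likely when 3B and 3C are true. These figures depend on the assumed 11/11 split and on bivariate normality; the critical r and the interval around zero depend only on n = 11.

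The absence of a PWV comparison is a lesser matter. The high-level versus low-level comparison is the one that both wordings of the aim support. The data to be collected are sound, so this should be fixed but does not threaten the study.

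**What to change.** Keep the planned correlations and add to the 3B/3C analysis paragraph:

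(a) *The correlation of change in renin with supine PWV will be reported separately in each group with a 95% CI. The difference between high-level SCI and each other group will be reported as an estimate with a 95% CI (Fisher z), with group-specific slopes and the SD of change in renin beside it.*

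(b) *Significance in one group and not in another will not be read as a group difference, nor non-significance as absence of a relationship.*

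As a secondary addition: *Supine PWV will be reported by group, with pairwise differences and 95% CIs.*

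The cost is analysis wording only, since group, renin and supine PWV are already collected. The downside is wide intervals. With two Fisher z contrasts, at least one would exclude zero about 9% of the time when all correlations are equal, so they should be labelled as estimates and not as confirmatory tests.
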